**Treatment Groups and Major Patient Populations for Analysis Periods for Study RHBY**

Abbreviations: ITT = intent-to-treat; IXE = ixekizumab; IXE-Structure = patients from Ixekizumab Structure Population; IXE80Q2W = ixekizumab 80 mg every 2 weeks; IXE80Q4W = ixekizumab 80 mg every 4 weeks; PBO = placebo; RW = randomized withdrawal; Total IXE = IXE80Q2W and IXE80Q4W combined in RHBY; vs. = versus.

- a IXEQ2W is a group of patients who have been treated consistently with ixekizumab 80 mg every 2 weeks since Week 0 in the originating studies through Week 64 of RHBY. IXEQ4W is a group of patients who have been treated consistently with ixekizumab 80 mg every 4 weeks since Week 0 in the originating studies through Week 64 of RHBY.

### **6.1.2. General Considerations for Analyses during the Combined Periods 1, 2, and 3**

Combined Periods 1 and 2 starts at the first injection of IXE80Q2W or IXE80Q4W in RHYB, and ends on the injection date of Week 64 (Group A: Visit 10/Group B: Visit 515) or next injection date after Week 64 if injection date of Week 64 is missing which is the start date of Period 3, or at ETV prior to Week 64.

Combined Periods 1, 2, and 3 starts at the first injection of IXE80Q2W or IXE80Q4W in RHYB, and ends on the date of Week 104 visit (Group A: Visit 14/Group B: Visit 519) or at ETV prior to Week 104.

#### **6.1.2.1. Lead-In Period Safety Population**

Safety data will be summarized for Combined Periods 1 and 2 and Combined Periods 1, 2, and 3 for the Lead-In Period Safety Population by Combined Ixekizumab treatment group (Total IXE) and each of the IXE80Q2W and IXE80Q4W groups without inferential statistics.

For safety analyses, unless otherwise specified, the following baselines will be used:

- For treatment-emergent adverse events (TEAEs):
  - For patients who were not randomized to placebo at Week 24 during the Combined Periods, the baseline is the events ongoing prior to the first injection in Period 1;
  - For patients who are randomized to placebo at Week 24 and then are retreated with ixekizumab, the baseline for TEAEs during Period 1 is the events ongoing just prior to the first injection in Period 1, but the baseline for TEAEs after retreatment of ixekizumab is the events ongoing just prior to the first injection of retreatment during Periods 2 and 3 Combined.
- For change from baseline to minimum/maximum postbaseline, to last observation and to each scheduled postbaseline visit for laboratory and vital signs, and for treatment-emergent abnormal laboratory and vitals, the baseline is the last nonmissing value prior to the first injection in Period 1, regardless of changes of treatment regimen after Week 24.

The categorical safety measures will be summarized with frequency counts and incidence rates.

#### **6.1.2.2. Long-Term Ixekizumab Treatment Efficacy Population**

Efficacy and health outcome data will be summarized for the Long-Term Ixekizumab Treatment Efficacy Population (see definition in Section 6.1.1) from Week 0 in the originating study to the visit at Week 64 and Week 104, respectively, in RHYB. For patients who were escalated from ixekizumab 80 mg Q4W to ixekizumab 80 mg Q2W after Week 64, only data while on ixekizumab 80 mg Q4W will be included. If the patient early terminates the originally assigned treatment (including retreatment and escalation) prior to Week 104, then the modified nonresponder imputation (mNRI) method will be applied for categorical endpoints, and modified baseline observation carried forward (mBOCF) will be applied for continuous endpoints from the early termination visit through Week 104.

The long-term treatment effect on a categorical variable is measured by the proportion of patients who have achieved or maintained a response (see algorithm in [Table RHY.6.4](#)) through Week 64 and Week 104, respectively, and the long-term treatment effect on a continuous variable is measured by change (or percent improvement) from baseline in the originating study.

The long-term treatment effect in categorical variables using observed cases, and continuous variables using observed cases and mBOCF will be summarized (as described in Section [6.1](#)) by treatment group (see [Table RHY.6.1](#)) at each scheduled visit from Week 0 in originating study. An alternative method to handle the missing data after Week 64 for the period of Week 0 in the originating study to Week 104 in RHY, mNRI method will be applied for categorical variables and mixed model for repeated measures (MMRM) will be applied for continuous variables. Data will also be summarized graphically using the response rate for categorical variables and mean for continuous variables by group at each scheduled visit. The time points during the Extension Period (Period 2) will follow the scheduled visits for group A patients with between-visits-interval of 8 weeks.

When the MMRM is used, the model will include treatment, originating study, geographic region, baseline value, visit, baseline value-by-visit, and treatment-by-visit interaction as fixed factors. The covariance structure to model the within-patient errors will be unstructured. The restricted maximum likelihood (REML) will be used. The Kenward-Roger method will be used to estimate the denominator degrees of freedom. The least-squares (LS) means will be reported to assess the maintenance of treatment effect; the 95% CI will also be reported. If the unstructured covariance matrix results in a lack of convergence, the heterogeneous Toeplitz covariance structure, followed by the heterogeneous autoregressive covariance structure, followed by the compound symmetry will be used. This order is specified according to a decreasing number of covariance parameters in the structure. The sandwich estimator (Diggle et al. 1994) for the covariance estimation will be used by specifying the EMPIRICAL option in SAS PROC MIXED. When sandwich estimation is used, the Kenward-Roger approximation for denominator degrees of freedom cannot be used. Instead, DDFM= BETWITHIN option will be used to estimate denominator degrees of freedom.

### ***6.1.3. General Considerations for Analyses during the Extension Period Including the Double-Blind RW Period (Period 2)***

#### **6.1.3.1. RW ITT and RW Safety Populations**

For patients who are randomized in Period 2 (group B), comparisons between Combined Ixekizumab treatment group and placebo, as well as between each ixekizumab regimen (80 mg Q2W or 80 mg Q4W) and placebo, will be performed for all analyses at each scheduled visit in Period 2 including Visit 515 at Week 64.

Period 2 starts at the first injection of study treatment after randomization (at Week 24) and ends at the following study events:

- Prior to the first injection of study treatment at Week 64 (Visit 515) for not retreated patients who have completed visit at Week 64. If injection at Week 64 is missing, the next injection date after Week 64 is used;
- Prior to the first injection of retreatment for patients who have been retreated within Period 2;
- ETV prior to Week 64.

For patients who are in the RW ITT Population and have been retreated with the ixekizumab treatment regimen due to a flare or any other reasons, only data prior to the time of the retreatment will be included in the analysis for Period 2. Data after retreatment will be imputed using nonresponder imputation (NRI) method for categorical variables and mBOCF method for continuous variables.

The observed values after retreatment will be used for other specified analysis, for example, efficacy analysis for Flare Population with Retreatment.

For efficacy and health outcomes, baseline is defined as the last available value before the first dose of study treatment in Period 2 from the originating study and, in most cases, will be the value recorded at Week 0 from the originating study.

The primary analysis method for treatment comparisons of categorical binary efficacy and health outcome variables will be a logistic regression with treatment group, geographic region, and originating study as factors using PROC Logistic with Wald method. The odds ratio and 95% CIs will be reported; treatment difference and 95% CI will also be reported. In the case when logistic regression model does not produce statistical results due to sparse data, Fisher's exact test will be used. Same analysis will also be carried out at each of other scheduled visits in Period 2.

The Kaplan-Meier product limit method will be used to estimate the survival curves for time (from Week 24 in RHBY) to flare. The number of patients at risk and experiencing flare by each scheduled visit during Period 2 will be presented by treatment group. The Kaplan-Meier estimate of the proportion of patients experiencing flare will be presented for each scheduled visit. Treatment group comparisons will be performed using the log-rank test with strata of geographic region and originating study. A Kaplan-Meier plot of time to the first flare by treatment group will also be provided.

Time to the first flare is defined as:

$$\begin{aligned} \text{Time to the first flare (weeks)} &= (\text{Date of the first flare during the analysis period} \\ &\quad - \text{Date of the randomization at Week 24} + 1)/7 \end{aligned}$$

Patients completing the treatment period without flare will be censored at the date of completion of the analysis period (eg, for Period 2, it is the date of Week 64 injection, or the last scheduled visit in the period if Week 64 injection date is missing). Patients without flare and a date of treatment period completion or a date of discontinuation will be censored at date of last dose in

the treatment period or date of last attended visit in the treatment period (scheduled or unscheduled), whichever is later.

Figures showing the proportion of patients not-experiencing flare at each scheduled visit within each treatment group will be provided. Figures showing the proportion of patients with ASAS20, ASAS40, ASAS partial remission, BASDAI50 and ASDAS inactive disease at each scheduled visit within each treatment group may also be provided.

The primary analyses for the continuous efficacy and health outcomes variables (see derivation in Sections 6.10.4 and 6.11) will be analyzed using analysis of covariance (ANCOVA) with mBOCF for missing data. The model will include treatment, Week 24 value, baseline value, geographic region, and originating study. Type III sums of squares for the LS means will be used for the statistical comparison; the 95% CI will also be reported.

For variables that are not collected at each postrandomization visit due to early discontinuation visits, data may exist at visits where the variable is not scheduled to be collected. Such data will be used in shift analyses, change from baseline to mBOCF endpoint analyses and other categorical analyses for the RW ITT and Safety Populations.

For safety analysis for the RW Safety Population, baseline is defined as the last nonmissing assessment prior to the first injection of study treatment in Period 2.

Fisher's exact test will be used for all adverse event (AE), discontinuation, and other categorical safety data. Continuous vital sign and laboratory values will be analyzed by an ANCOVA with treatment and baseline value in the model.

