## 5.2. Determination of Sample Size

It is estimated that approximately 750 patients will enter the long-term extension study (RHBY) after completion of Studies RHBV, RHBW, or RHBX. This sample size is estimated based on the 1-year retention rates from ixekizumab psoriasis studies and from 1 secukinumab radiographic (rad)-axSpA study (Baeten et al. 2015), which had a retention rate of approximately 85%. It is anticipated that approximately 30% of the 750 patients will meet the entry criteria for randomized-withdrawal (Sieper et al. 2015). Approximately 100 patients who achieved a state of sustained remission on IXE80Q4W will be randomized in a 2:1 ratio to IXE80Q4W or placebo, and approximately 100 patients who achieved a state of sustained remission on IXE80Q2W will be randomized in a 2:1 ratio to IXE80Q2W or placebo in the double-blind RWR period. This total sample size of 200 will provide over 99% power to detect a difference in the proportion of patients who do not experience a flare between the Combined Ixekizumab treatment group (including Q2W and Q4W) and placebo using a 2-sided Fisher's exact test at the 0.05 level, assuming the flare rates are 10% for ixekizumab and 70% for placebo. Sample size and power calculations are calculated using nQuery+nTerim 3.0.

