## 5.3. Method of Assignment to Treatment

During the Lead-In Period (Period 1), patients who are previously receiving ixekizumab treatment during Studies RHBV and RHBW will, as of Week 0 in Study RHBY, continue to receive the same ixekizumab treatment regimen they are on at the end of the originating study, but now in open-label fashion.

For patients who are previously in Study RHBX, treatment during the Lead-In Period will be assigned as follows:

- patients who are rescued to open-label IXE80Q2W will remain on IXE80Q2W in open-label fashion.
- patients who are receiving blinded treatment with either IXE80Q2W or IXE80Q4W will continue on their ixekizumab dose regimen in blinded fashion.
- patients who are receiving blinded treatment with placebo will be assigned to receive blinded treatment with IXE80Q4W.

During the Extension Period, including RWR (Period 2), patients in Group A who do not meet entry criteria for RWR will continue to receive the same ixekizumab dose regimen that they are receiving during the Lead-In Period (IXE80Q2W or IXE80Q4W).

During the Extension Period, patients in Group B who have achieved a state of sustained remission, and meet the criteria for randomized withdrawal (RW) (see Section 5.1), will be assigned to treatment groups as follows by a computer-generated random sequence using an interactive web-response system (IWRS).

- Patients in the IXE80Q2W treatment group will be re-randomized to either IXE80Q2W or placebo at 2:1 ratio allocation and will be stratified by region and originating study.

- Patients in the IXE80Q4W treatment group will be re-randomized to either IXE80Q4W or placebo at 2:1 ratio allocation and will be stratified by region and originating study.

The IWRS will be used to assign double-blind investigational product to each patient. Site personnel will confirm that they have located the correct investigational product package by entering a confirmation number found on the package into the IWRS.

During the Long-Term Extension Period (Period 3), patients will continue the same treatment that they are receiving at the end of Period 2.

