**Table RHBY.6.1. Treatment Groups and Major Patient Populations for Analysis Periods for Study RHBY**

Population	Period	Analyses	Treatment Groups	Group Comparisons
Lead-In Period Safety Population	Combined Periods 1 & 2 Combined Periods 1, 2, & 3	Safety	IXE80Q2W IXE80Q4W Total IXE	Descriptive No inferential statistics
Long-Term Ixekizumab Treatment Efficacy Population	Combined Periods 1 & 2 Combined Periods 1, 2, & 3	Efficacy and health outcomes	IXE80Q2W a IXE80Q4W a Total IXE	Descriptive No inferential statistics
RW Safety Population	Period 2 Period 3	Safety	IXE80Q2W IXE80Q4W Total IXE Placebo	Total IXE vs. Placebo IXE80Q2W vs. Placebo IXE80Q4W vs. Placebo
RW ITT Population	Period 2 Combined Periods 2 & 3	Efficacy and health outcomes	IXE80Q2W IXE80Q4W Total IXE Placebo	Total IXE vs. Placebo IXE80Q2W vs. Placebo IXE80Q4W vs. Placebo
Ixekizumab Structure Population	At Week 56 for a 2-year assessment	Efficacy	IXE80Q2W IXE80Q4W Total IXE	Descriptive No inferential statistics
Flare Population with retreatment	Period 2, Combined Periods 2 and 3	Efficacy	PBO/IXE80Q2W PBO/IXE80Q4W PBO/IXE IXE80Q2W/IXE80Q2W IXE80Q4W/IXE80Q4W IXE/IXE	Descriptive No inferential statistics
Dose Escalation Population	Period 3	Efficacy	PBO/IXE80Q4W, IXE80Q4W/ IXE80Q4W Total	Descriptive No inferential statistics
Follow-Up Population	Period 4	Safety	IXE80Q2W IXE80Q4W Total IXE Placebo	Descriptive No inferential statistics

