## 6.5. Multiple Comparisons/Multiplicity

The following is a list of primary and major secondary objectives to be tested during Period 2:

1. Primary – proportion of patients who do not experience a flare (Total IXE versus Placebo)
2. Secondary 1 – proportion of patients who do not experience a flare (IXE80Q4W versus Placebo)
3. Secondary 2 – time to the first flare (Total IXE versus Placebo)
4. Secondary 3 – time to the first flare (IXE80Q4W versus Placebo)

A multiple testing strategy using graphical multiple testing procedure (Bretz et al. 2011) for the primary and major secondary objectives will be implemented to control the family-wise type I error rate at a 2-sided  $\alpha$  level of 0.05.

The primary and major secondary endpoints will be sequentially tested in the order, as presented in Figure RHBY.6.1 using the primary statistical method described in Section 6.1.3.1 to compare ixekizumab with placebo. This is a predetermined fixed testing order; thus it is a gatekeeper method. If a test in this sequence is not significant, all the subsequent tests will be considered non-significant (Hsu and Berger 1999). The graphical approach is a closed testing procedure; hence, it strongly controls the family-wise error rate (Hsu and Berger 1999; Alos et al. 2014).

Abbreviations: IXE = ixekizumab; Combined IXE = IXEQ2W + IXWQ4W; Q2W = every 2 weeks; Q4W = every 4 weeks.

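### The two Q4W tests in the alpha-controlled sequence use placebo patients from both re-randomisations, so they rest on an unstated assumption of equal placebo flare risk by lead-in dose

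*SAP*

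**What the plan says.** SAP 5.3 describes two parallel randomisations. Patients on Q4W at the end of the lead-in "will be re-randomized to either IXE80Q4W or placebo at 2:1 ratio allocation", and patients on Q2W are separately re-randomised 2:1 to Q2W or placebo. Both are stratified by region and originating study.

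The analysis does not follow that split. SAP 6.1.3.1 says comparisons of the combined group with placebo, "as well as between each ixekizumab regimen (80 mg Q2W or 80 mg Q4W) and placebo, will be performed for all analyses". For the RW ITT Population, Table RHBY.6.1 lists one placebo group and the comparisons "Total IXE vs. Placebo IXE80Q2W vs. Placebo IXE80Q4W vs. Placebo". The binary endpoint is analysed by "a logistic regression with treatment group, geographic region, and originating study as factors using PROC Logistic with Wald method". For time to flare, "Treatment group comparisons will be performed using the log-rank test with strata of geographic region and originating study". Lead-in dose appears in neither.

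SAP 6.5 places two Q4W contrasts in the controlled sequence: Secondary 1, the "proportion of patients who do not experience a flare (IXE80Q4W versus Placebo", and Secondary 3, the time-to-flare equivalent. It says of the procedure, "hence, it strongly controls the family-wise error rate".

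**The concern.** Secondary 1 and 3 compare about 67 Q4W patients with about 67 placebo patients. Only about 33 of those controls were randomised against Q4W; the rest come from the Q2W randomisation. A graphical procedure controls family-wise error only if each component test is valid under its own null. Randomisation alone does not make these two valid. They also need equal placebo flare risk across lead-in doses, conditional on region and originating study.

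That equality cannot be presumed:

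- Lead-in dose is not purely a randomised factor. Under Protocol 5.1, RHBX patients rescued to Q2W stay on Q2W, and RHBX patients still on blinded placebo all go to Q4W. Adjusting for originating study does not remove a difference between doses within RHBX.
- Entry to the randomised withdrawal requires remission on the lead-in dose, so the two placebo groups were also selected on different regimens.

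If Q2W-origin placebo patients flare more often, part of that excess is read as a Q4W benefit. If they flare less often, Q4W is disadvantaged.

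**Working it through.** **Inputs.** SAP 5.2: about 100 patients per lead-in dose, 2:1 allocation, 2-sided 0.05, Fisher's exact test, "assuming the flare rates are 10% for ixekizumab and 70% for placebo". So each randomisation gives about 67 active and 33 placebo. The documents give no placebo rate by lead-in dose, so these are assumed and varied.

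**The plan's own figure.** Exact Fisher power for 133 v 67 at 10% v 70% exceeds 99.99% (stated: over 99%). For 100 v 50, the 150-patient case in Protocol 10.1, it also exceeds 99.99% (stated: over 95%). Both reproduce.

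**Bias in the Q4W contrast.** Let p4 and p2 be the placebo flare rates for Q4W-origin and Q2W-origin patients. With 33 + 34 controls, the expected pooled placebo rate is (33·p4 + 34·p2)/67, so the bias is (34/67)·(p2 − p4) = 0.507·(p2 − p4). A 10-point gap moves the contrast by about 5 points. At the planning rates (Q4W 10%, p4 = 70%):

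- p2 = 50%: (23.1 + 17.0)/67 = 59.9%, a difference of about 50 points instead of 60.
- p2 = 90%: (23.1 + 30.6)/67 = 80.1%, a difference of about 70 points.

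**Error of Secondary 1 when Q4W has no effect** (Q4W and its own placebo both at 50%; nominal 5%, 2-sided). The SAP model was simulated with 40,000 replicates per scenario, assuming RHBV 45%, RHBW 20%, RHBX 35% and Europe 60%. The Monte Carlo standard error at 5% is √(0.05·0.95/40,000) = 0.11 points. The unadjusted Wald test was enumerated exactly for 33 + 33 and 33 + 34 controls.

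| p2 − p4 | SAP model, 2-sided | Exact unadjusted, 2-sided | Of which favouring Q4W |
|---|---|---|---|
| 0 | 5.0% | 4.7–5.6% | 2.3–2.8% |
| +5 | 6.3% | 5.6–6.6% | 4.5–5.2% |
| +10 | 9.2% | 8.5–9.6% | 8.0–9.0% |
| +20 | 21.6% | 20.6–22.0% | 20.6–21.9% |
| −10 | 9.0% | 8.5–9.6% | 0.5–0.6% |
| −20 | 22.2% | 20.6–22.0% | 0.1% |

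Further results:

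- Gap only in RHBX (35% of patients): 5.6%, 6.9% and 9.8% for gaps of 10, 20 and 30 points.
- Different study mix by dose, no within-study gap: 5.2%. Originating study in the model handles that part.
- Null rate of 70% (exact, unadjusted): 4.8–5.0% with no gap, 5.9–6.2% at +5, 9.4–9.9% at +10.
- Own controls only, 67 v 33: 4.7% unadjusted and 5.3% adjusted, whatever p2 is.
- Secondary 3 (log-rank, 20,000 simulated trials, exponential flare times, 4-weekly visits, no strata): 5.2%, 9.2% and 22.5% for gaps of 0, 10 and 20 points; own control 4.9–5.1%.
- Testing the primary first gives little protection. With Q2W effective (10% flare on drug) and Q4W null at p4 = 50%, p2 = 70%, false claims for Q4W are 21.8%, against about 2% with own controls.

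**Primary test.** Allocation is 2:1 in both randomisations, so lead-in dose is balanced between the combined ixekizumab and placebo groups. For 133 v 67 with the two strata 0 to 20 points apart, the exact error is 4.4–4.6%.

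**The case against.** The strongest reply has four parts.

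- **No documented gap.** The only placebo rate is a single 70%, both strata enter on the same ASDAS criteria, and some patients' lead-in dose traces back to Week 0 randomisation in the originating study. The one mechanism named in the documents is confined to RHBX, where the inflation is much smaller. This stands as a limit on size. It does not supply the missing assumption, because the single rate is a planning value and entry is selected on remission.
- **One-sided harm.** The objectives are superiority. When Q2W-origin placebo flares less often, false claims for Q4W fall below 2.5%. This is right: the negative-gap rows show bias against Q4W, not false superiority.
- **A comparability issue, not a multiplicity flaw.** The graphical procedure itself is sound. True, but the strong-control statement covers two component tests whose validity randomisation does not guarantee.
- **The plan partly looks at this.** Table RHBY.6.1 separates placebo by retreatment dose in the descriptive Flare Population, and SAP 6.14.1 has length-of-exposure subgroups and allows further exploratory ones. But no visible analysis compares placebo flare rates by lead-in dose with the matching denominators. The table of planned exploratory analyses is not in the public text, so nothing can be said about it.

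The reply also notes that own controls cost power. That is real and is given with the fix.

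**Conclusion.** The concern holds. The textual point is firm: there are two randomisations, one placebo comparator and no lead-in-dose term, and no visible text states or justifies equal placebo risk. The size depends on assumed dose-specific rates and an assumed study mix. False superiority arises only if Q2W-origin placebo patients flare more often: 2-sided error is about 6% for a 5-point gap, 9% for 10 and 22% for 20 across all studies, and 5.6% to 9.8% if a gap of 10 to 30 points is confined to RHBX.

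The primary test and Secondary 2 are not confounded. At the planning rates the Q4W conclusion would hardly change: rejection stays at or above 99.98% for p2 from 30% to 90%. The effect estimate could still shift by about 10 points either way for a 20-point gap. This should be fixed, but it does not threaten the main conclusion.

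**What to change.** In SAP 6.1.3.1, 6.5 and Tables RHBY.6.1 and RHBY.6.5, define Secondary 1 and Secondary 3 as IXE80Q4W versus patients re-randomised from Q4W to placebo. For consistency, base the Q2W contrasts, which lie outside the controlled sequence, on Q2W-origin placebo. Keep the pooled-placebo contrasts as sensitivity analyses with the equal-risk assumption stated, and report placebo flare rates by lead-in dose. Adding lead-in dose as a factor or stratum in the combined analyses would match the randomisation but is optional.

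No new data are needed, because lead-in dose determines which randomisation a patient entered. Protocol 10.3.1.2.1 should be aligned, or the change explained in the clinical study report as Protocol 10.3.1 allows.

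The cost is a halved control group for the dose-specific tests. At 10% v 70%, Fisher power is still 99.999% (67 v 33) and 99.97% (50 v 25, the 150-patient case). For smaller effects, moving from 67 v 67 to 67 v 33 lowers Fisher power from 94.6% to 82.8% at 20% v 50% (Wald 96.3% to 86.4%), and from 79.2% to 65.6% at 10% v 30% (Wald 83.2% to 69.6%).

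If the sponsor prefers to keep pooled placebo as the main contrast, the minimum is to state the assumption and add the own-control analysis and the placebo rates by lead-in dose. That gives transparency but does not restore the randomised basis of the two tests.

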10.1. Sample Size Determination

Approximately 100 patients who achieved a state of sustained remission on ixekizumab Q4W will be randomized in a 2:1 ratio to ixekizumab 80 mg Q4W or placebo, and approximately 100 patients who achieved a state of sustained remission on ixekizumab Q2W will be randomized in a 2:1 ratio to ixekizumab 80 mg Q2W or placebo in the double-blind randomized withdrawal-retreatment period. This 200 total sample size will provide over 99% power to detect a difference in the proportion of patients who do not experience a flare between ixekizumab treatment (including both Q2W and Q4W) and placebo using a 2-sided Fisher's exact test at the 0.05 level, assuming the flare rates are 10% for ixekizumab and 70% for placebo. It is estimated that approximately 30% of total enrolled patients (i.e., approximately 200 patients) will meet the criteria to enter the double-blind randomized withdrawal-retreatment period.

If less than the anticipated number of patients meet the criteria to enter the double-blind randomized withdrawal-retreatment period (e.g., 20%), the total number of patients (approximately 150) would still provide over 95% power to detect a difference between ixekizumab treatment and placebo in the proportion of patients who do not experience a flare.

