- Patients in the ixekizumab 80 mg Q2W treatment group (IXE80Q2W) will be re-randomized to either IXE80Q2W or placebo at 2:1 ratio and will be stratified by geographic region (see [Table RHBY.6.2](#)) and originating study.
- Patients in the ixekizumab 80 mg Q4W treatment group (IXE80Q4W) will be re-randomized to either IXE80Q4W or placebo at 2:1 ratio and will be stratified by geographic region (see [Table RHBY.6.2](#)) and originating study.

After completion of the 40-week RWR period, patients will continue the same treatment that they are receiving at the end of Period 2, and will continue in the Long-Term Extension Period (Period 3).

Patients who have taken at least 1 study dose and who discontinue study treatment are to complete an early termination visit (ETV) and enter into Post-Treatment Follow-Up Period (Period 4) for at least 12 weeks and up to 24 weeks after the ETV date or the last regularly scheduled visit. Patients whose ETV or last regularly scheduled visit is longer than 12 weeks after their last study dose are not required to enter into the Post-Treatment Follow-Up Period.

[figure not shown]

Figure RHBY.5.1. Illustration of study design for Clinical Protocol I1F-MC-RHBY.

(footnotes on next page)

Abbreviations: Q2W = once every 2 weeks; Q4W = once every 4 weeks; W = week.

- a Patients in Group A will continue to receive the same ixekizumab dose regimen that they were receiving during Period 1.
- b Only patients having achieved a state of sustained remission (Group B) are eligible for participation in the randomized withdrawal–retreatment period.
- c Patients who experience a flare will be retreated with the ixekizumab treatment regimen that they were receiving prior to withdrawal. Flare status is determined by ASDAS score ([Table RHY.6.4](#)). The interactive web-response system uses the flare status to dispense drug. Therefore, no missing data is allowed before discontinuation. If a component score is missing (eg, missing C-reactive protein due to COVID-19 mitigation plan) at an intermittent visit, the last nonmissing score is carried forward for the assessment.

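### With 2:1 allocation and no unequal-variance provision, the Period 2 ANCOVA intervals for Total IXE v placebo are expected to be somewhat too narrow for flare-driven scores

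*SAP*

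**What the plan says.** SAP 6.1.3.1 analyses continuous efficacy and health outcomes in the randomized withdrawal population by ANCOVA with mBOCF. The terms are treatment, the Week 24 value, the baseline value, region and originating study. On inference it adds only: "Type III sums of squares for the LS means will be used for the statistical comparison; the 95% CI will also be reported". Tables RHBY.6.5 and RHBY.6.7 apply this model to Total IXE v placebo and to each dose v placebo, at each scheduled Period 2 visit.

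Allocation is 2:1 in both dose strata: about 100 patients "will be randomized in a 2:1 ratio to IXE80Q4W or placebo", and about 100 "will be randomized in a 2:1 ratio to IXE80Q2W or placebo in the double-blind RWR period". The sample size is set "assuming the flare rates are 10% for ixekizumab and 70% for placebo".

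Under SAP 6.3.3, a patient retreated after a flare keeps the last value before retreatment. A patient who stops because of an adverse event gets the originating-study baseline.

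The only robust variance estimator in the SAP belongs to the long-term MMRM (6.1.2.2). Neither document gives an SD by arm for any continuous outcome.

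**The concern.** An ordinary ANCOVA estimates one residual variance for both arms. With equal arms, unequal spread hardly matters. With 2:1 allocation it does: the pooled estimate is dominated by the larger arm, so if the smaller arm is the more variable one, the standard error of the difference is too small.

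This design points in that direction for scores that follow flare. Patients enter Period 2 in sustained remission. A flare needs ASDAS of at least 2.1 at two consecutive visits, or above 3.5 once (SAP Table RHBY.6.4), and the value before retreatment is then carried forward. Later values in each arm therefore mix remission and flare states, and a 70/30 mixture is more spread out than a 10/90 mixture. What is at stake is whether intervals reported as 95% for ASDAS, BASDAI, patient global, spinal pain and similar scores have that coverage.

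**Working it through.** **1. The plan's own figure.** SAP 5.2 says "This total sample size of 200 will provide over 99% power to detect a difference", using Fisher's "exact test at the 0.05 level, assuming the flare rates are 10% for ixekizumab and 70% for placebo". Exact enumeration at 133 v 67 gives power above 99.99%, so the statement reproduces. Protocol 10.1 says 150 patients "would still provide over 95% power to detect a difference between ixekizumab treatment and placebo"; at 100 v 50 the power is also above 99.99%. These checks confirm the arm sizes and flare rates used below but say nothing about the ANCOVA.

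**2. Formulas.** Let V_I and V_P be the arm variances, with n_I = 133 and n_P = 67.
- True SE² = V_I/133 + V_P/67.
- Expected pooled SE² = [(132·V_I + 66·V_P)/198]·(1/133 + 1/67).
- k = pooled SE / true SE. Approximate coverage = 2Φ(1.96k) − 1.

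At exactly 2:1, k² = (2V_I + V_P)/(V_I + 2V_P): pooling attaches each variance to the other arm's sample size. The ratio does not depend on total N, so it is essentially the same at 150 patients.

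**3. By SD ratio (placebo/ixekizumab).** Simulated four-covariate ANCOVA, 10,000 runs each:

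| SD ratio | True SE / pooled SE | Coverage, pooled | Coverage, HC3 |
|---|---|---|---|
| 0.8 | 0.93 | 96.6% | 95.6% |
| 1.0 | 1.00 | 94.6% | 95.1% |
| 1.25 | 1.08 | 93.2% | 95.3% |
| 1.5 | 1.14 | 91.6% | 95.1% |
| 2.0 | 1.22 | 89.0% | 95.0% |

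**4. Linking the ratio to the planned flare rates.** Flare status has variance 0.1 × 0.9 = 0.09 v 0.7 × 0.3 = 0.21. From flare status alone the SD ratio is at most √(0.21/0.09) = 1.53. If flare shifts a score by D within-state SDs, with equal within-state spread, the ratio is √[(1 + 0.21D²)/(1 + 0.09D²)]. For D = 1, 2 and 3 this gives 1.05, 1.16 and 1.26, with coverage of about 94.6%, 93.8% and 93.1%.

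**5. ASDAS example (assumed: remission mean 1.1, SD 0.4; flare mean 2.8, SD 0.6).** The separation is 1.7 and 1.7² = 2.89.
- V_I = 0.9 × 0.16 + 0.1 × 0.36 + 0.09 × 2.89 = 0.44.
- V_P = 0.3 × 0.16 + 0.7 × 0.36 + 0.21 × 2.89 = 0.91.
- Pooled SE² = 0.0134; true SE² = 0.0168; k = 0.89; coverage 91.9%.

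Simulations of this case with covariates gave 91.4% to 92.6% pooled and 95.0% to 95.8% with HC3. With a common within-state SD of 0.5 or 0.6 the formula gives 92.8% or 93.2%.

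**6. Adding the adverse-event rule.** Assume baseline ASDAS 3.8 (SD 0.8), carried forward for the same fraction of each arm and taken from the remission share. With the step 5 SDs:
- 3%: variances 0.64 v 0.94, coverage 93.4%.
- 5%: variances 0.76 v 0.96, coverage 94.1%.

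With a common SD of 0.5 and 5%, coverage is 94.7%. The documents give no adverse-event discontinuation rate.

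**7. Intermediate visits.** The documents give no flare rates by visit. Assume 5% v 40%, with the step 5 means and SDs:
- V_I = 0.95 × 0.16 + 0.05 × 0.36 + 0.0475 × 2.89 = 0.31.
- V_P = 0.6 × 0.16 + 0.4 × 0.36 + 0.24 × 2.89 = 0.93.
- k = 0.84; coverage 90.2% (simulated 90.1%; HC3 95.2%).

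A common SD of 0.5 or 0.6 gives 91.2% or 91.8%. Adding 3-5% adverse-event carry-forward to the step 5 SDs gives 92.0-92.8%.

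**8. Direction.** With equal within-state spread, 30% v 70% gives equal variances and no error. At 30% v 80% the SD ratio is below 1 and the intervals are slightly wide.

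**The case against.** The strongest reply is that the placebo SD is nowhere stated. A reader might infer that placebo is the more variable arm and that the intervals are too narrow. The documents do not establish this. They give flare rates, and the rest is an assumption about means and spread. This stands, and the conclusion is worded as an expectation at the planned rates.

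A reader might also infer that the test rejects too often. That does not follow. In this mechanism unequal spread comes only from unequal flare rates, which also move the means. With equal rates (10/10 or 70/70) the variances match and k = 1. At the planned rates the ASDAS difference is 0.6 × 1.7 = 1.02, about 8.8 pooled standard errors or 7.9 true ones, so the decision is the same.

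Nor do the documents support extending the effect to every continuous outcome. ASDAS defines flare and is close to the most favourable case. Nothing here shows the effect for BASMI, chest expansion or SF-36. Each dose v placebo is about 67 v 67: fitted pairwise there is no distortion, and in a three-arm model k is about 0.94 on the step 5 figures.

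The adverse-event carry-forward rule also shrinks the effect, as step 6 shows. Against that, 10% and 70% are whole-period rates, and the separation of variances can be larger at intermediate visits (step 7).

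**Conclusion.** The point holds in limited form. The Period 2 ANCOVA has no unequal-variance provision under 2:1 allocation, and the plan's flare rates and carry-forward rule make placebo the arm expected to vary more on flare-driven scores. The Total IXE v placebo intervals for those scores are then expected to fall short of 95% coverage by roughly 0.5 to 5 percentage points. The shortfall depends on visit, flare separation and adverse-event discontinuations, all of which are assumed here.

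The primary and major secondary comparisons use logistic regression and the log-rank test (SAP 6.5, 6.10.1, 6.10.2) and are untouched. The outcomes concerned are other secondary and health outcomes without multiplicity adjustment. The change is worth considering because it is cheap, not because a main conclusion is at risk.

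**What to change.** In SAP 6.1.3.1, keep the ANCOVA mean model and add one sentence: for the Period 2 continuous comparisons, standard errors and intervals use HC3, or arm-specific residual variances (PROC MIXED, REPEATED / GROUP=treatment, Satterthwaite degrees of freedom). HC3 coverage was 95.0-95.6% at every SD ratio in step 3, so the choice does not require knowing which arm varies more. The arm-specific option was not simulated here.

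The cost is one line of text and one procedure option. HC3 leaves the treatment estimate unchanged. Intervals for flare-driven scores widen, by up to about 12-15% in the base case (1/0.89 = 1.12 analytically; simulated HC3 SE 0.131 against model SE 0.114 = 1.15).
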